4.2.2.2 Supportive secondary endpoints

Supportive secondary efficacy endpoints

EudraCT no.: 2016-000878-38

- Change from baseline in fasting plasma glucose (FPG) 16 weeks after randomisation
- If a subject achieves HbA_{1c} targets 16 weeks after randomisation:
 - \circ HbA1c < 7.0%
 - o HbA1c < 7.0% without severe hypoglycaemia
- Change from baseline in 30- minutes, 1- hour, 2- hour, 3- hour and 4- hour PPG and 30-minutes, 2- hour, 3- hour and 4- hour PPG increment 16 weeks after randomisation (meal test)
- Change from baseline in endpoints derived from the 7-9-7-point self-measured plasma glucose (SMPG) profile 16 weeks after randomisation:
 - o Mean of the 7-9-7-point profile
 - o Postprandial glucose and PPG increment (mean, breakfast, lunch, main evening meal)
 - o Fluctuation in 7-9-7-point profile
 - o Change in the nocturnal SMPG measurements
- If a subject achieves PPG target (overall mean of daily PPG measurements in 7-9-7-point SMPG profile) 16 weeks after randomisation:
 - o Overall PPG (1 hour) \leq 7.8 mmol/L [140 mg/dL]
 - Overall PPG (1 hour) \(\leq 7.8 \) mmol/L [140 mg/dL] without severe hypoglycaemia
- Insulin dose (Units/day and Units/kg/day; total basal, total bolus and individual meal insulin dose) 16 weeks after randomisation
- Change from baseline in lipids-lipoproteins profile 16 weeks after randomisation (total cholesterol, high density lipoproteins (HDL) cholesterol, low density lipoproteins (LDL) cholesterol)

| Protocol | Date: 23 February 2018 | **Novo Nordisk** | Trial ID: NN1218-4113 | Version: 4.0 | Status: Final |

Page:

20 of 112

Supportive secondary safety endpoints

- Number of treatment emergent adverse events (AEs) during 16 weeks after randomisation
- Number of treatment emergent injection site reactions during 16 weeks after randomisation
- Number of treatment emergent hypoglycaemic episodes classified both according to the ADA definition and Novo Nordisk definition during 16 weeks after randomisation
 - Overall

EudraCT no.: 2016-000878-38

- o Daytime hypoglycaemic episodes
- Nocturnal hypoglycaemic episodes (00:01-05:59 inclusive)
- Hypoglycaemic episodes from start of meal until 1, 2, 4 hours and from 2 hours (exclusive) to 4 hours (inclusive) after start of meal
- Change from baseline in clinical evaluations 16 weeks after randomisation:
 - Physical examination
 - Vital signs (diastolic blood pressure, systolic blood pressure and pulse)
 - Electrocardiogram
 - Fundoscopy/fundus photography

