8.4.2 Hypoglycaemic episodes

Plasma glucose should always be measured and recorded when a hypoglycaemic episode is suspected.

All plasma glucose (PG) values:

- $\leq 3.9 \text{ mmol/L} (70 \text{ mg/dL}) \text{ or}$
- > 3.9 mmol/L (70 mg/dL) occurring in conjunction with hypoglycaemic symptoms

should be reported in the diary by the subject from Visit 2 to Visit 32 (FU2) and in the eCRF by the investigator according to the instructions below.

Upon onset of a hypoglycaemic episode the subject is recommended to measure PG every 15 minutes until the SMPG value is >3.9 mmol/L (70 mg/dL) and/or symptoms have been resolved in accordance to current guidelines. 34

A SMPG value ≤3.9 mmol/L (70 mg/dL) or hypoglycaemic symptoms must trigger a hypoglycaemic episode form to be completed by the subject. Repeated SMPG measurements and/or symptoms, occurring within a period of 60 minutes after onset on a hypoglycaemic episode, will by default be considered as one hypoglycaemic episode until a succeeding SMPG value is >3.9

 Protocol
 Date:
 23 February 2018
 Novo Nordisk

 Trial ID: NN1218-4113
 Version:
 4.0
 4.0

 UTN: U1111-1180-0636
 Status:
 Final
 Final

 EudraCT no.: 2016-000878-38
 Page:
 49 of 112
 49 of 112

mmol/L (70 mg/dL) and/or symptoms have been resolved and should be reported on one hypoglycaemic episode form. SMPG measurements ≤3.9 mmol/L (70 mg/dL) or hypoglycaemic symptoms after the 60 minutes period shall trigger the reporting of a new hypoglycaemia episode and prompt the subject to fill out a new hypoglycaemic episode form until a succeeding measurement is >3.9 mmol/L (70 mg/dL) and/or symptoms have been resolved.

In case of several low SMPG values within the 60 minutes interval, the lowest value is the one that will be reported as the SMPG value for the hypoglycaemic episode but the start time of the episode will remain as the time for the first SMPG value and/or symptom.

The record should include the following information:

- Start date and time of the hypoglycaemic episode
- The PG level before treating the episode (if available) and any follow up measurements. The lowest value measured during the hypoglycaemic episode will be reported as the PG value for the episode, the remaining values will be kept as source data in the diary.
- Whether the episode was symptomatic (Yes/No)
 A hypoglycaemic episode starting without symptoms should be updated to symptomatic if the subject experiences symptoms later during the episode.

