- Whether the subject was able to treat him/herself
- If the severity of a hypoglycaemic episode aggravates, only one hypoglycaemic episode should be reported reflecting the most severe degree of hypoglycaemia. Date, time and dose of last bolus insulin administration prior to the episode
- Date, time and dose of last basal administration prior to the episode
- Date and time of last main meal (not including snacks) prior to the episode
- Whether the episode occurred in relation to physical activity
- Change in any concomitant illness
- Any sign of fever and/or other acute disease
- Whether the subject was asleep when the episode occurred
- If yes, whether the symptoms of the episode woke up the subject

The answer to the question: "Was the subject able to treat him/herself?" must be answered "No" for an episode requiring assistance of another person to actively administer carbohydrate, glucagon, or take other corrective actions. Plasma glucose concentrations may not be available during an event, but neurological recovery following the return of PG to normal is considered sufficient evidence that the event was induced by a low PG concentration. 34

Oral carbohydrates must not be given if the subject is unconscious.

 Protocol
 Date:
 23 February 2018
 Novo Nordisk

 Trial ID: NN1218-4113
 Version:
 4.0
 4.0

 UTN: U1111-1180-0636
 Status:
 Final
 Final

 EudraCT no.: 2016-000878-38
 Page:
 50 of 112
 50 of 112

If the question "Was the subject able to treat him/herself?" is answered "No", the following information should be recorded by the subject:

- Who assisted in the treatment of the hypoglycaemic episode (i.e. medical person or non-medical person)?
- Where the treatment was administered (in clinic/emergency room/hospital or other. If the subject was treated in clinic/emergency room/hospital, whether they were transported in an ambulance or not)
- Type of treatment provided by another person (i.e. oral carbohydrates, glucagon, IV glucose or other)
- Were symptoms alleviated after administration of treatment?
- Factors contributing to the episode (i.e. physical activity, missed meal, diet change, medication error (i.e. overdose, mix-up between products, incorrect use of device), miscalculation of dose of antidiabetic medication, other factors not listed or unknown)
- Did the subject experience seizure?
- Was the subject unconscious/comatose?

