1.2 Scope of the statistical analysis plan

This statistical analysis plan (SAP) is based on the protocol *Efficacy and Safety of Fast-acting Insulin Aspart Compared to NovoRapid*[®] *both in Combination with Insulin Degludec with or without Metformin in Adults with Type 2 Diabetes (onset*[®] *9*), version 4.0 (dated 23 February 2018). The statistical analyses and derivations of endpoints presented in this SAP are almost identical to those described in the protocol. It contains minor clarifications for derivations, calculation of endpoints and analyses as well as some additions.

The changes to the statistical considerations proposed in this SAP and the reasons for the changes are described in section $\underline{3}$ and will be reported in the clinical trial report (CTR).

Statistical Analysis Plan Trial ID: NN1218-4113 UTN: U1111-1180-0636 EudraCT No.: 2016-000878-38

CONFIDENTIAL

Date: Version: Status: Page:

12 February 2019 | Novo Nordisk Final 6 of 29

Statistical considerations 2

General considerations

In general, for endpoints evaluated as a change from baseline and/or where a baseline adjustment is made, baseline is defined as information collected at randomisation (Visit 14). In case a measurement is not available at randomisation, the most recent measurement prior to randomisation will be used as baseline.

Two observation periods are defined, "in-trial" and "on-treatment", and it will be specified which period each analysis will use.

- In-trial: The observation period from date of randomisation and until last trial -related subject-site contact. The in-trial observation period includes data collected after treatment discontinuation.
- On-treatment: The observation period from date of first dose of randomised NovoRapid[®]/faster aspart and to 7 days after the first occurrence of:
 - The day of last dose of randomised NovoRapid ®/faster aspart
 - The day before initiation of ancillary treatment

All efficacy endpoints will be summarised and analysed using the full analysis set (FAS), unless otherwise stated. Safety endpoints will be summarised using the safety analysis set and analysed using the FAS, unless otherwise stated. The FAS and safety analysis set are defined in section 2.2.

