Presentation of results from a statistical analysis will include the estimated mean treatment effects (LSMeans) for change from baseline, if applicable. Estimated mean treatment differences (or ratios) will be presented together with two-sided 95% confidence interval (CI) for all endpoints analysed statistically.

Data collected before randomisation (Visit 14) will only be summarised descriptively.

Testing strategy and estimands

The primary objective of the trial is to confirm the effect of treatment with faster aspart compared to NovoRapid[®], both in combination with insulin degludec with or without metformin in adults with T2DM in terms of glycaemic control, using a non-inferiority approach.

More specifically the upper limit of the 95% confidence interval for the difference between faster aspart and NovoRapid® should be compared to a non-inferiority margin of 0.4%. If it is below or equal to 0.4% non-inferiority will be considered established and effect demonstrated.

The trial also aims to confirm superiority of treatment with faster aspart for a number of secondary confirmatory endpoints. The family-wise type I error rate will be controlled in the strong sense

 Statistical Analysis Plan
 Date:
 12 February 2019
 Novo Nordisk

 Trial ID: NN1218-4113
 Version:
 2.0

 UTN: U1111-1180-0636
 Status:
 Final

 EudraCT No.: 2016-000878-38
 Page:
 7 of 29

using a hierarchical (fixed sequence) testing procedure under the framework of the primary estimand. This is based on a priority ordering of the null-hypotheses, and testing them in this order using the two-sided 95% confidence interval approach until an insignificant result appears. The effect is that rejection of a null hypothesis only will be considered for analyses where all previous null-hypotheses have been rejected in favour of faster aspart.

The steps in the hierarchical testing procedure are as follows:

- Step 1 (Primary analysis): HbA_{1c} non-inferiority of faster aspart versus NovoRapid[®]
- Step 2: 1-hour PPG increment (meal test) superiority of faster aspart versus NovoRapid®
- Step 3: HbA_{1c} superiority of faster aspart versus NovoRapid®
- **Step 4**: 1,5-anhydroglucitol superiority of faster aspart versus NovoRapid[®]

Primary estimand

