2.4.2.2 Safety endpoints

In terms of AEs, as a minimum, SAEs will be tabulated separately using the in-trial observation period.

All events in the in-trial observation period will be listed with information about whether it appeared in the on-treatment observation period or not.

Number of treatment emergent adverse events

Adverse events (AEs) will be coded using the Medical Dictionary for Regulatory Activities (MedDRA). AEs will be presented based on system organ class and preferred terms.

A Treatment Emergent Adverse Event (TEAE) is defined as an event that has an onset date on or after the first day of exposure to randomised treatment, and no later than seven days after the last day of exposure to randomised treatment.

TEAEs are summarised descriptively, whereas AEs not defined as treatment emergent are presented in listings, including AEs reported in the 30-day follow-up period. The summaries of TEAEs are made displaying the number of subjects with at least one event, the percentage of subjects with at least one event, the number of events and the event rate per 100 patient years of exposure. These summaries are done by seriousness, severity, relation to insulin treatment, relation to technical complaint, premature treatment discontinuation due to AEs, and outcome.

Furthermore, summary tables based on system organ class and preferred terms are made for:

All TEAEs

- Serious TEAEs
- Possibly or probably related TEAEs
- Severe TEAEs
- TEAEs with preferred term that are experienced by at least 5% of the subjects in any treatment arm or by at least 5% of all subjects

For AEs where additional information is recorded, this will be listed.

AEs occurring during the run-in period are considered non-treatment emergent and will be summarised separately.

Number of treatment emergent injection site reactions

Treatment emergent injection site reactions occurring during the trial will be summarised and listed.

Classification of Hypoglycaemia

Treatment emergent: hypoglycaemic episodes will be defined as treatment emergent if the onset of the episode occurs on or after the first day of exposure to randomised treatment, and no later than one day after the last day of exposure to randomised treatment.

Nocturnal hypoglycaemic episodes: episodes occurring between 00:01 and 05.59 both inclusive.

[figure not shown]

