Hypoglycaemic episodes are classified according to the Novo Nordisk classification of hypoglycaemia (see Figure 2–1) and the ADA classification of hypoglycaemia (see Figure 2–2).

Novo Nordisk classification of hypoglycaemia

In normal physiology, symptoms of hypoglycaemia occur below a PG level of 3.1 mmol/L (56 mg/dL). Therefore, Novo Nordisk has included hypoglycaemia with PG levels below this cut-off point in the definition of BG confirmed hypoglycaemia.

Novo Nordisk uses the following classification (see Figure 2–1) in addition to the ADA classification:

- Severe hypoglycaemia according to the ADA classification.⁴
- Severe or BG confirmed hypoglycaemia: An episode that is severe according to the ADA classification⁴ or BG confirmed by a PG value <3.1 mmol/L (56 mg/dL) with or without symptoms consistent with hypoglycaemia.

[figure not shown]
Note: Glucose measurements are performed with capillary blood calibrated to plasma equivalent glucose values

BG: blood glucose PG: plasma glucose SMPG: Self-measured plasma glucose

Figure 2–1 Novo Nordisk classification of hypoglycaemia

ADA classification⁴ of hypoglycaemia

- Severe hypoglycaemia: An episode requiring assistance of another person to actively administer carbohydrate, glucagon, or take other corrective actions. Plasma glucose concentrations may not be available during an event, but neurological recovery following the return of PG to normal is considered sufficient evidence that the event was induced by a low PG concentration.
- Asymptomatic hypoglycaemia: An episode not accompanied by typical symptoms of hypoglycaemia, but with a measured PG concentration ≤ 3.9 mmol/L (70 mg/dL).
- Documented symptomatic hypoglycaemia: An episode during which typical symptoms of hypoglycaemia are accompanied by a measured PG concentration ≤ 3.9 mmol/L (70 mg/dL).
- Pseudo-hypoglycaemia: An episode during which the person with diabetes reports any of the typical symptoms of hypoglycaemia with a measured PG concentration > 3.9 mmol/L (70 mg/dL) but approaching that level.
- Probable symptomatic hypoglycaemia: An episode during which symptoms of hypoglycaemia are not accompanied by a PG determination but that was presumably caused by a PG concentration ≤ 3.9 mmol/L (70 mg/dL).

Note: Glucose measurements are performed with capillary blood calibrated to plasma equivalent glucose values PG: plasma glucose SMPG: Self-measured plasma glucose

Figure 2–2 ADA classification of hypoglycaemia

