Treatment emergent hypoglycaemic episodes are presented in terms of the number of subjects with at least one event (N), the percentage of subjects with at least one event (%), the number of events (E) and the event rate per 100 years of exposure (R). Separate summaries are made by severity considering all episodes, nocturnal and daytime episodes using Novo Nordisk and ADA classified episodes. All episodes will also be summarised by category, including summaries in relation to time since start of meal, as occurring within the following time intervals:

- During first 1, 2, and 4 hours after start of meal
- Between 1 (exclusive) to 2 hours (inclusive) after start of meal
- Between 2 (exclusive) to 3 hours (inclusive) after start of meal
- Between 3 (exclusive) to 4 hours (inclusive) after start of meal
- Between 2 (exclusive) to 4 hours (inclusive) after start of meal

The number of treatment emergent severe or BG confirmed hypoglycaemic episodes (all, daytime, nocturnal, 1 hour, 2 hours, 4 hours, 1 (exclusive) to 2 hours (inclusive), 2 (exclusive) to 3 hours (inclusive), 3 (exclusive) to 4 hours (inclusive), and 2 (exclusive) to 4 hours (inclusive) after start of the meal) will be analysed based on the FAS using a negative binomial regression model with a log-link function and the logarithm of the time period in which a hypoglycaemic episode is considered

Statistical Analysis Plan		Date:	12 February 2019	Novo Nordisk
Trial ID: NN1218-4113	CONFIDENTIAL	Version:	2.0	
UTN: U1111-1180-0636		Status:	Final	
EudraCT No.: 2016-000878-38		Page:	25 of 29	

treatment emergent as offset. The model will include treatment, region and metformin use at baseline (Yes/No) as factors. To the extent where data allow, separate analysis will be performed for severe hypoglycaemic episodes (all).

Change from baseline in clinical evaluations 16 weeks after randomisation:

Physical examination

The physical examination parameters (head, ears, eyes, nose, throat, neck, respiratory system, cardiovascular system, gastrointestinal system incl. mouth, musculoskeletal system, central and peripheral nervous system, skin), and their change from baseline, will be summarised descriptively using the on-treatment period. All findings will be listed.

Vital signs

Vital signs include diastolic blood pressure, systolic blood pressure and pulse. The measurements will be summarised descriptively using the on-treatment period and both actual values as mean change and change from baseline.

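### Does leaving the run-in hypoglycaemia rate out of the models for overall, daytime and nocturnal episodes weaken the safety comparison?

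*SAP*

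**What the plan says.** SAP section 2.4.2.2, like Protocol v4.0 section 17.4.2.2, fits a negative binomial model with log link to the number of treatment-emergent severe or BG confirmed episodes in the FAS, with log time at risk as offset. "The model will include treatment, region and metformin use at baseline (Yes/No) as factors". The SAP lists ten such counts: overall, daytime, nocturnal and seven windows after the start of a meal. Protocol section 4.2.2.2 places them under "Supportive secondary safety endpoints", outside the four-step hierarchy.

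Two rules in SAP section 2 (General considerations) bear on earlier data. The first is that "Data collected before randomisation (Visit 14) will only be summarised descriptively". The second is that baseline is the Visit 14 value and, where that is not available, "the most recent measurement prior to randomisation will be used as baseline".

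The ingredients of a run-in rate are nevertheless collected. Under Protocol v4.0 section 8.4.2, low glucose values and symptomatic episodes "should be reported in the diary by the subject from Visit 2 to Visit 32 (FU2"). Even the reduced run-in record in Protocol v2.0 section 8.4.2 keeps start date and time, the glucose value and whether the subject could self-treat. That is enough to classify an episode as severe or "BG confirmed by a PG value <3.1 mmol/L (56 mg/dL) with or without symptoms consistent with hypoglycaemia" and to pick out nocturnal ones, "episodes occurring between 00:01 and 05.59 both inclusive".

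**The concern.** A subject's past rate of hypoglycaemia is a natural predictor of the later rate. The continuous efficacy models in the SAP adjust for the baseline value of their own endpoint, and the hypoglycaemia models do not. Comparing safety is a stated objective, and an earlier T2DM trial described in Protocol section 3.1.3 found no significant difference in the overall rate. Where no difference is the likely result, interval width decides which differences can be ruled out, so an unused covariate looks like avoidable loss of precision.

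The point can only concern three of the ten counts. A run-in version of the post-meal counts needs "Date and time of last main meal (not including snacks) prior to the episode", which the v2.0 reduced record did not collect during run-in.

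**Working it through.** **1. Is the planned estimate valid without the covariate?** Let A be the arm, X the log run-in rate and t the exposure, with E[Y | A, X] = t·exp(α + βA + γX). Randomisation makes X independent of A. Averaging over X gives E[Y | A] = t·exp(α + βA)·E[exp(γX)]. The log rate ratio β is the same with or without X, and the variation due to X goes into the dispersion.

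A simulation of the planned model (536 per arm, 10% stopping early, 200 trials per setting) agrees. The mean error in β lay between −0.013 and 0.022, and a nominal 5% test rejected in 1.5% to 8% of runs. With 200 runs a true 5% has a Monte Carlo standard error of √(0.05 × 0.95/200) = 1.5 percentage points, so these rates scatter around 5%.

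**2. The plan's own figures.** There is no power or precision figure for hypoglycaemia. The 536 per arm comes from step 2 of the hierarchy: (0.6/3.5) × √(536/2) = 2.806; 2.806 − 1.960 = 0.846; Φ(0.846) ≈ 0.80. The noncentral t gives 80.06%, against 80.1% stated. The sample size therefore does not lean on these models.

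**3. What could be gained?** With full exposure and equal rates, the planned variance is roughly (2/n)(1/μ + k), where μ is the mean count and k the dispersion. For assumed μ = 1 and k = 1.5 this is (2/536)(1 + 1.5) = 0.00933, so SE = 0.0966. The simulated value is 0.0981, because 10% have shortened exposure.

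A second simulation (400 trials per setting) added the matching run-in rate. Its assumptions were 1–3 episodes per subject per 16 weeks, dispersion 1.5–3, and 80% daytime and 20% nocturnal. The table shows the fall in the SE of the log rate ratio by assumed run-in-to-treatment correlation:

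| Count | 0.3 | 0.5 | 0.7 |
|---|---|---|---|
| Overall, all run-in data usable | 0.7–2.0% | 2.1–5.6% | 4.7–12.2% |
| Daytime, all usable | 0.6–1.7% | 1.7–5.1% | 3.7–10.7% |
| Nocturnal, all usable | 0.1–0.7% | 0.3–2.0% | 0.7–4.5% |
| Overall, 60% of subjects partly on the withdrawn system | 0.4–1.1% | 1.2–3.1% | 2.4–6.4% |
| Daytime, same | 0.3–1.0% | 0.9–2.8% | 1.9–5.8% |
| Nocturnal, same | 0.1–0.4% | 0.2–1.1% | 0.4–2.5% |

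At correlation 0 nothing is gained or lost. Adjusted and planned mean log rate ratios differ by at most 0.005.

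The simulation in step 1 covered a wider range (0.3–4 episodes, dispersion 1.5–4, correlation 0.3–0.8). The variance fell by 0.4% to 38%. In SE terms, 1 − √0.996 = 0.2% and 1 − √0.62 = 21%.

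**4. Where is this trial likely to sit?** Protocol Appendix A titrates basal insulin in run-in while subjects stay on their own bolus analogue (sections 3.2 and 3.3). After randomisation the bolus insulin is switched and titrated, and basal is held (sections 3.4 and 3.5). Amendment 2 withdrew the first meter and eDiary because of an unusual reporting pattern for hypoglycaemia and glycaemic values. Protocol v4.0 section 8.3.2 then has those subjects on an alternative meter until the new one arrives, with no rule there for recording episodes in the gap. Each of these weakens the link between run-in and treatment counts, so a gain of 1–2% of SE is a reasonable reading, and under 1% for nocturnal episodes.

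**5. What does 1–2% look like?** Take SE 0.0981 and an observed ratio of 1.00. The upper 95% limit is exp(1.96 × 0.0981) = 1.212. With SE 1% smaller it is exp(1.96 × 0.0971) = 1.210; with SE 2% smaller, exp(1.96 × 0.0961) = 1.207.

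**The case for a change.** The strongest case for a change is that the covariate costs no new data. An SE smaller by 1–2% is worth 1/0.99² − 1 = 2.0% to 1/0.98² − 1 = 4.1% more subjects, about 22 to 44 of 1072. SAP section 2.5 already adds a supplementary model for the meter switch, but only for HbA1c. If episodes are frequent and correlation is high, the gain could be well above 2%; the documents cannot exclude it.

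The arithmetic stands, and so does derivability from the v2.0 and v4.0 records. Protocol v3.0, which amendment 2 amends, is not in the file. The conclusion does not follow, for three reasons.

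- A supplementary model leaves the main intervals exactly as wide as before, so it does not cure the alleged loss.
- Putting the covariate in the main model would reverse the SAP's rule on pre-randomisation data. The fallback for a missing Visit 14 value does not cover this: it replaces one measurement with the latest earlier one, whereas an episode count has no Visit 14 value and the covariate would be an event rate accumulated over 12 weeks.
- That covariate would carry counts from the withdrawn system. If exposure is taken as Visit 2 to randomisation, any uncaptured gap weeks stay in the denominator. Section 8.3.2 asks only for the start date of the new meter, so the length of the gap is not shown to be recoverable.

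Nor would it help with the first two hours after a meal, where the earlier T2DM trial saw more episodes, because the post-meal models cannot use it for all subjects.

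**Conclusion.** The concern does not hold. The planned rate ratios are valid and unbiased, the model is fully specified, and leaving out the run-in rate agrees with the SAP's own rule. The most that can be said is that some precision may be given up: 0.1% to 12.2% of the standard error under one set of assumptions, about 0.2% to 21% under a wider one, and probably 1–2% overall and under 1% for nocturnal episodes. Every one of these figures rests on assumed event rates, dispersion and correlation, since the documents state none. The validity argument needs only randomisation and the log link, provided that exposure time does not depend on the run-in rate differently by arm. For a supportive safety endpoint outside the hierarchy, with run-in counts of doubtful quality, adjusting for them or not is a matter of preference, and the plan's choice is sound.
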